We will estimate the effect of PECS/SAP blocks on FEV_1 , FVC and peak flow rate using three separate repeated measures regression models with an autoregressive correlation structure, adjusting for baseline FEV_1 , FVC, peak flow rate and imbalanced confounders (if any).

The Wald tests for regression model coefficients will be used to test each of the secondary hypotheses; the Bonferroni correction for four outcomes will be employed to control the overall Type I error rate at 0.05 for the secondary outcomes.

Exploratory Analysis

Two separate linear regression models will be developed to assess the relationship between analgesia strategy and each of the two exploratory outcomes (quality of recovery after anesthesia survey and persistent postoperative surgical pain). To compare patients from two groups on these outcomes mean difference will be reported along with 95% confidence intervals.

Descriptive and Safety Analyses

We will summarize descriptive and safety outcomes by randomized groups using appropriate summary statistics (i.e., mean \pm standard deviation, median [Q1, Q3], or N (%) as appropriate). No statistical tests will be performed on these outcomes.

Sample Size Considerations

Per Mamoun, observed a coefficient of variation (CV) of 53% in the placebo group of cardiac surgery patients.⁵⁹ We assumed a slightly more conservative CV of 50% and that the treatment effect favored PECS/SAP blocks by 20% (i.e., true ratio of geometric means of 0.80). We will need to enroll approximately 192 patients (96 per group) to have 90% power at the 0.05 significance level to detect superiority of PECS/SAP blocks to standard routine parenteral and enteral analgesia in patients recovering from MICS .

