We also plan for two interim analyses at 1/3 and 2/3 of the planned enrollment to assess safety, feasibility and formal efficacy and futility. Therefore, interim adjusted sample size is N=98 patients per group, or N=196 total. We will use the conservative gamma spending function with parameters -5 and -5 for alpha (efficacy) and beta (futility), respectively. If the alternative hypothesis is true (the treatment effect exists) there will be a cumulative probability of 10%, 53% and 100% of crossing either an efficacy or futility boundary at the 1st, 2d and final analyses, respectively (Table A and Figure 1 below contains boundary Information). Planned first and second interim analyses will be performed upon accrual of 66 and 132 patients respectively. **Therefore, planned number of patients for the analysis is N=98 patients per group, or N=196 total.**

We will also enroll at least 5 pilot patients in the beginning of the study to test the feasibility of protocol adherence and data collection.

Table A. Boundary Information for interim analysis (3 analyses = 3 stages):

Boundary Information (Standardized Z Scale)**Null Reference = 0**

Stage	Information Level	Alternative		Boundary Values				
		Reference	Lower	Lower	Upper	Beta	Beta	
	Proportion	Lower	Upper	Alpha	Beta	Beta	Alpha	
1		0.3333	-1.88730	1.88730	-3.18319	-0.02167	0.02167	3.18319
2		0.6667	-2.66904	2.66904	-2.64022	-0.53609	0.53609	2.64022
3		1.0000	-3.26890	3.26890	-1.97517	-1.97517	1.97517	1.97517

Figure 1. Boundary plot

[figure not shown]

Table 1: Patient demographic and preoperative risk factors

Sex
Age (years)
Surgery Type (Robot MVR, thoracotomy MVR, AVR through RAT)
Coronary Artery Disease
Hypertension
Pervious Myocardial infarction
Peripheral Arterial Disease
Previous vascular surgery
Smoker (current or former)
Cerebrovascular disease
Diabetes mellitus

Renal failure: Indicate whether the patient has 1) a documented history of renal failure and/or 2) a history of creatinine > 2.0. Prior renal transplant patients are not included as pre-op renal failure unless since transplantation their creatinine has been or currently is > 2.0.
Left ventricular EF

Table 2: Surgical, intraoperative and postoperative data

Time on CPB
X-clamp time
RBCs
Plt
FFP
Cryo
Inotropes in the OR
Time to extubation
Length of ICU stay
Length of hospital stay

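### The sample size calls a CV of 50% more cautious than the observed 53%, but it is less cautious; at 53% the stated 90% power is about 87.6%

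*Combined protocol and SAP*

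**What the plan says.** All of the relevant text is under Sample Size Considerations.

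- The source trial "observed a coefficient of variation (CV) of 53% in the placebo group of cardiac surgery patients".
- The planning value follows in the next sentence: "We assumed a slightly more conservative CV of 50% and that the treatment effect favored PECS/SAP blocks by 20"%, which the text also expresses as a "true ratio of geometric means of 0.80".
- The resulting size: "We will need to enroll approximately 192 patients (96 per group) to have 90% power at the 0.05 significance level".
- After allowance for two interim analyses with efficacy and futility boundaries, the "planned number of patients for the analysis is N=98 patients per group, or N=196 total". The text adds that, if the assumed effect is real, the cumulative chance of crossing a boundary is 10% at the first look and 53% at the second.

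The 53% is the only CV the plan cites. It gives no reason for planning below it, other than describing the lower value as the cautious one.

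**The concern.** In a sample size calculation, a cautious variability assumption is one that is larger than the evidence suggests, because it leads to more patients. Going from 53% to 50% shrinks the assumed variance and the sample size. The sentence therefore tells the reader that a safety margin was added when a small one was removed.

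More than wording is at stake if the 50% produced the patient number. In that case the 90% power and the interim stopping probabilities are more favourable than the plan's own evidence supports. A null result would then be presented as coming from a 90%-powered trial sized on a cautious assumption.

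**Working it through.** **Inputs**

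- CV assumed 50%, CV observed 53%, ratio of geometric means 0.80, alpha 0.05, power 90%, 96 and then 98 per group: Sample Size Considerations.
- Log-transformed OBAS, reported as a geometric mean ratio: Primary analysis.
- Two-sided testing: not stated in words; inferred from the symmetric lower and upper boundaries in Table A (final values ±1.97517).
- Interim looks at 1/3 and 2/3, with boundaries from Table A.

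**Log-scale quantities**

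- Effect: |ln 0.80| = 0.2231.
- SD on the log scale = sqrt(ln(1 + CV²)).
  - CV 50%: sqrt(ln 1.25) = sqrt(0.2231) = 0.4724.
  - CV 53%: sqrt(ln 1.2809) = sqrt(0.2476) = 0.4976.

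**Step 1: reproduce the plan's own figure (CV 50%)**

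n per group = 2 × (1.9600 + 1.2816)² × SD² / effect² = 2 × 10.507 × 0.2231 / 0.2231² = 94.2, so 95 by the normal approximation. With the t distribution it is 96, the plan's number, with power 90.3%. Other readings do not give 96: one-sided 0.05 gives 77, and using the CV directly as the log-scale SD gives 106.

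Table A also reproduces. Its drift of 3.2689, run through its boundaries, gives power 90.0%, type I error 0.050, and cumulative stopping of 10.0% and 53.4%. The inflation over a fixed design is (3.2689 / 3.2415)² = 1.017, and 96 × 1.017 = 97.6, hence 98. The method is therefore identified.

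**Step 2: change only the CV, to 53%**

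- Fixed design: 2 × 10.507 × 0.2476 / 0.2231² = 104.5, so 105 per group (normal approximation), or 106 with the t distribution.
- With the interim looks: 2 × (3.2689 × 0.4976 / 0.2231)² = 106.3, so 107. Scaling the t-based 106 by 98/96 gives 108.

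**Step 3: power at the planned size**

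Under the group-sequential design, drift = 0.2231 / (SD × sqrt(2/98)), which is 3.307 at CV 50% and 3.139 at CV 53%.

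| Per group | Design | CV 50% | CV 53% |
|---|---|---|---|
| 96 | fixed, t-test | 90.3% | 87.1% |
| 98 | fixed, t-test | 90.8% | 87.8% |
| 98 | Table A boundaries | 90.6% | 87.6% |

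At 98 per group and CV 53%, cumulative stopping under the alternative is 8.9% at the first look and 49.7% at the second, against the stated 10% and 53%.

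**The case against.** **The calculation is internally correct.** At a CV of 50%, 96 and 98 per group both follow, and a sponsor may choose its planning value. That stands. What fails is the description of 50% as the cautious choice, and the absence of any other reason for it.

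**The trial may have more power than a single-measure calculation shows.** The primary hypothesis concerns OBAS over three days, analysed with a repeated-measures model, and the plan does not say whether the 53% describes one day or a three-day average. Suppose it describes one day and the test is on the three-day mean with autoregressive correlation. Power at 98 per group, CV 53% and the Table A boundaries would then be about 97.8%, 94.8%, 92.7% and 90.3% for adjacent-day correlations of 0.5, 0.7, 0.8 and 0.9. If 53% already describes an average, 87.6% stands. The documents do not settle this. However, the plan's own calculation uses a single CV with no such gain, and under either reading 50% is less cautious than 53%. The 87.6% should be read as the plan's stated power recomputed at its source figure, not as a forecast of the power of the final model.

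**Enrolment was later raised.** The version history records a rise to 208 to replace 12 patients converted to sternotomy, then to about 214 to increase power. At CV 53% with the Table A boundaries, power is 90.2% if all 214 are analysed (107 per group). It is 88.5% if the 12 conversions are not analysed, leaving 202 (101 per group). The increase could therefore recover most or all of the loss. The current sample size text still sets 196 for analysis and still rests on 50%, so the statement needs correcting either way.

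**The effect is small.** It is about 2.4 points of power, and no boundary, alpha level or analysis rule changes. That is true, and it limits the weight of the point.

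**Conclusion.** The statement is wrong as written. A CV of 50% is less cautious than the 53% the plan cites, and the 96 and 98 per group depend on it. At 53%, with 98 per group and the Table A boundaries, power for a ratio of 0.80 is about 87.6%. The false-negative risk is about 12.4% rather than 10%, close to a quarter more in relative terms. Holding 90% would take 107 to 108 per group, 9 or 10 more than planned.

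These figures assume two-sided testing at 0.05, one log-normal measure per patient as in the plan's own calculation, equal groups, and 196 patients analysed. The direction of the error depends on none of these. The finding does not invalidate the design or show that the trial must be enlarged.

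**What to change.** Delete the claim that 50% is the more cautious value and give power at both values. For example: with 98 patients per group and the planned interim boundaries, power to detect a geometric mean ratio of 0.80 is about 91% if the CV is 50% and about 87.6% if it is 53%, as in the cited trial; the 50% assumption is the less conservative of the two. State the interim stopping probabilities as conditional on the CV in the same way (10% and 53% as given; about 9% and 50% at a CV of 53%).

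If more than 196 patients are analysed, quote the power at 53% for that number: 88.5% for 202 and 90.2% for 214. It would also help to say whether the 53% refers to one day or a three-day average.

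The cost is a sentence or two and a slightly less favourable power figure. No patients are added, and the boundaries and analysis stay as they are.
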